## 9.0 STATISTICAL CONSIDERATIONS AND DATA MANAGEMENT

### 9.1 General Considerations

To test our hypotheses, we will use intention-to-treat (ITT) analysis of covariance models to test for treatment group differences in Week 24 levels of inflammation biomarkers adjusted for baseline levels. P-values will be two-sided and considered significant at  $\alpha=0.05$ . Adjustments for multiple comparisons will not be performed due to the relatively small sample size and exploratory nature of this phase II trial.

In secondary/exploratory analysis, multivariable linear regression models will be constructed to include treatment group and other potentially confounding baseline and time-updated variables that differ significantly between groups and which may account for differences in outcomes. Baseline characteristics that may be included in the models are demographics (age, sex, race/ethnicity), ISI scores, PHQ-9 and SCL-20 scores, tobacco/adherence questionnaire results, ART drugs/regimens (including efavirenz, rilpivirine, and integrase inhibitors), insomnia medication use, comorbidities, CD4 cell counts, HIV-1 RNA levels, levels of the inflammation biomarkers, and nonprescription substance use. Time-varying characteristics that may be included are changes in ISI scores, questionnaire results, CD4 cell counts, ART drugs/regimens, and HIV-1 RNA levels.

We will also perform ‘per protocol’ secondary analyses comparing the ISI4-6 subgroup (defined as participants who completed  $\geq 4$  of the 6 SHUTi sessions) vs. the active control group to determine if greater SHUTi engagement leads to greater differences in the endpoints of interest.

We will also examine relationships between changes in questionnaire scores, especially ISI scores, and the inflammatory endpoints using Pearson correlations.

All of these models will be repeated for comparing 12-week changes in the endpoints in addition to the primary models for 24-week changes.

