#### 9.5 Sample Size Justification

The goal of this application is to provide proof-of-concept data and effect sizes of SHUTi on inflammation/monocyte activation endpoints in support of a future, definitive trial. As such, the proposed sample size is based on the enrollment time period and the funding allowance of the R21 mechanism, not for definitive superiority testing. We will enroll 50 participants with the expectation that 40 (20 in each arm) will complete the 24 week study. Using the standard deviations and correlations between baseline and week 24 for hsCRP (this trial's primary endpoint) from our previously published depression trial, we have 80% power ( $\alpha=0.05$ ) to detect mean differences between study groups of 3.41 mg/L. This detectable difference is clinically meaningful, as it is similar to that found to be predictive of CVD events and overall mortality in the SMART trial (66, 110).

For the primary and secondary endpoints, the following table demonstrates the effect sizes that can be observed between study groups (N=20 in each arm), assuming similar variances and correlations as observed in our pilot trial of internet CBT for depression in PWH. Of note, the detectable difference in IL-6 is also clinically meaningful, given that differences of 1.3-2.2 pg/mL were associated with greater risks of CVD and mortality in the SMART trial (66, 110).

Outcome	SD	Correlation	Detectable mean difference (N=20 per group)
hsCRP (mg/L)	4.87	0.64	3.41
IL-6 (pg/mL)	2.34	0.32	2.02
sCD14 (ng/mL)	751	0.70	488
sCD163 (ng/mL)	19.12	0.89	7.97
%CD14+CD16+ monocytes	5.54	0.31	4.77

Our group has access to ~3000 HIV-positive outpatients engaged consistently in care within the Indiana University Health system (Eskenazi Health with 1200; IU Methodist Hospital with 1800). As part of our pilot trial, we found that ~30% of the virologically-suppressed PWH in our HIV clinics have ISI scores  $\geq 11$ . Thus, there are ~900 patients eligible for recruitment. Based on review of our clinic population characteristics, we estimate ~800 will fulfill the other eligibility criteria.

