#### 9.7 Patient Characteristics and Significant Protocol Violations

Demographic and other baseline data will be summarized descriptively for all patients in the ITT set. Comparisons between the two groups will be performed using Pearson's chi-square tests and Student's t-tests. Significant protocol violations will be documented.

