In secondary/exploratory analysis, multivariable linear regression models will be constructed to include treatment group and other potentially confounding baseline and time-updated variables that differ significantly between groups and which may account for differences in outcomes. Baseline characteristics that may be included in the models are demographics, ISI scores, tobacco/adherence questionnaire results, ART drugs/regimens (including efavirenz, rilpivirine, and integrase inhibitors), anti-insomnia medication use, comorbidities, CD4 cell counts, and HIV-1 RNA levels. Time-varying characteristics that may be included are changes in ISI scores, questionnaire results, CD4 cell counts, ART drugs/regimens, and HIV-1 RNA levels.

We will also perform 'per protocol' secondary analyses comparing the ISI₄₋₆ subgroup vs. the active comparator control group to determine if greater SHUTi engagement leads to greater differences in the endpoints of interest.

We will also examine relationships between changes in questionnaire scoring, especially ISI scores, and the inflammatory endpoints using Pearson correlations.

All of these models will be repeated for comparing 12 week changes in the endpoints in addition to the primary models for 24 week changes.

Missing Data Approach: Missing data mechanisms will be examined by comparing completers with incompleters on the baseline factors. Multiple imputation (SAS proc mi and mianalyze) will be used if a substantial amount (>10%) of missing data exist. Of note, our trial biostatistician ([name]) is an expert on longitudinal and missing data analysis, which are critical for contemporary trial analysis.

Sex as a Biological Variable: In exploratory analyses, we will examine sex as a potential moderator of treatment effects on all outcomes by testing treatment group x sex interactions. Given that the proposed trial is not powered to detect such interactions, models will also be run separately for males and females to assess whether there are clinically important differences in the treatment group-outcome relationships between sexes.

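### In the secondary adjusted models, baseline covariates are chosen partly by significance tests of between-arm imbalance, which is less precise than naming a few prognostic covariates in advance

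*Protocol*

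**What the plan says.** The primary analysis is fixed. Protocol 9.1 and the SAP (Statistical Analyses) use an intention-to-treat ANCOVA to "test for treatment group differences in Week 24 levels of inflammation biomarkers adjusted for baseline levels".

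A second layer follows. Protocol 9.1 states: "In secondary/exploratory analysis, multivariable linear regression models will be constructed". Besides treatment group, these models take in "other potentially confounding baseline and time-updated variables that differ significantly between groups and which may account for differences in outcomes". The SAP applies the same rule to "potentially confounding baseline and time-updated variables that differ significantly between groups and which may account for differences in outcomes".

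Both documents then list baseline characteristics that may enter. The protocol's list is longer: PHQ-9, SCL-20, inflammation biomarker levels and substance use appear there but not in the SAP. Neither document names a fixed set or says how the second condition, relevance to outcome, will be judged.

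Protocol 9.7 provides between-arm tests of baseline data in the ITT set: "Comparisons between the two groups will be performed using Pearson's chi-square tests and Student's t-tests". Randomisation is 1:1, stratified by sex and regular sleep-aid use (Protocol 3.3). Neither factor is stated as a fixed model term.

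**The concern.** This point concerns baseline variables only. Because allocation is random, any baseline difference between arms arises by chance. A significant difference therefore does not show that the variable affects hsCRP, and a non-significant one does not show that the imbalance is harmless. What makes adjustment useful is the covariate's association with the outcome, and the imbalance test does not measure that.

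Stratification should also hold sex and sleep-aid use near balance. The rule will therefore tend to leave out the two factors the design singled out.

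This matters because the trial's stated product is effect-size estimates for a later trial (Protocol 9.5), and Protocol 5.2 gives precise estimation as a reason for using an active control. The same models are repeated at Week 12 and extend to the other biomarkers.

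**Working it through.** **Inputs from Protocol 9.5 and 9.1.** hsCRP SD 4.87 mg/L; baseline to Week 24 correlation 0.64; 20 completers per arm; two-sided alpha 0.05; 80% power; detectable difference 3.41 mg/L.

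**Assumptions.** The documents do not give the number of candidates or how many are prognostic. I take 15 independent candidates and show 10 to 25. Prognostic strength is the share of residual variance explained once baseline hsCRP is in the model.

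**Step 1: reproduce the plan's figure.** Residual SD = 4.87 × √(1 − 0.64²) = 3.742. SE of the difference = 3.742 × √(2/20) = 1.183. The noncentral t with 37 df gives a detectable difference of 3.40 mg/L at 80% power, against 3.41 stated. The plan's figure is a baseline-adjusted ANCOVA calculation and does not involve the selection rule.

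**Step 2: what the test selects.** Each baseline variable is flagged with probability 0.05, prognostic or not. In simulation the rates were about 5% for both kinds. With k independent candidates, P(at least one flagged) = 1 − 0.95^k:

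| k | expected flagged | P(at least one) |
|---|---|---|
| 10 | 0.50 | 40% |
| 15 | 0.75 | 54% |
| 20 | 1.00 | 64% |
| 25 | 1.25 | 72% |

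Correlation among candidates and the near-balance of the stratification factors lower these figures: 13 candidates correlated at 0.3 give 43%.

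**Step 3: precision.** Simulated SD of the estimated hsCRP effect (mg/L), 20 per arm, baseline hsCRP always in the model, Monte Carlo error about 0.01. Only the imbalance test is coded as the selection rule.

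| Candidates | Imbalance test | Baseline only | Prognostic ones named in advance |
|---|---|---|---|
| 15, none prognostic | 1.26–1.27 | 1.19–1.20 | – |
| 15, one with partial r 0.3–0.5 | 1.23–1.26 | 1.19–1.20 | 1.06–1.16 |
| 15, two at 10% each | 1.24 | 1.19–1.20 | 1.09–1.10 |
| 15, two at 25% each | 1.20 | 1.20–1.22 | 0.88 |
| 6, three at 20% each | 1.12–1.14 | 1.20–1.21 | 0.79 |

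In the third row, power at 3.41 mg/L is 75% under the test, 79% with baseline only and 85% with the two named in advance.

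**Step 4: closed-form check.** With p covariates unrelated to arm and 40 patients, the variance is the residual variance × (2/20) × 37/(37 − p).

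- Baseline only (p = 1): 1.183 × √(37/36) = 1.20.
- One prognostic covariate added (p = 2), r = 0.3: 1.183 × √(1 − 0.09) × √(37/35) = 1.16.
- The same with r = 0.5: 1.183 × √(1 − 0.25) × √(37/35) = 1.05.

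These agree with the second row within simulation error.

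**Step 5: the test as a guard against imbalance.** Protocol 9.7 tests the ITT set, so 25 per arm. An imbalance of 0.45 SD gives t = 0.45 × √(25/2) = 1.59 on 48 df, p = 0.12, and is not selected. It would still shift the estimate by r × 0.45 × 3.742, which is 0.51 mg/L for r = 0.3 and 0.84 mg/L for r = 0.5. That is 15% to 25% of 3.41 mg/L.

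**The case against.** **The rule has two conditions.** A covariate must also be capable of explaining outcome differences, which could filter out noise. If that means a tested association with outcome at p < 0.05 (an assumption), noise variables enter about 0.2% of the time and prognostic ones 2% to 4%. Precision is then close to or better than baseline only. This stands as far as it goes, but the documents do not define the condition. Even on this reading a prognostic covariate is nearly always left out, and naming it in advance is more precise.

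**A reader might infer that the rule is always worse than no extra adjustment.** The documents do not support that. The loss appears when most candidates are noise or weak predictors. It vanishes with two strong predictors among 15, and reverses with three strong ones among six (1.12 to 1.14 against 1.20 to 1.21). With 15 candidates correlated at 0.3, four of them prognostic, rule and baseline-only ANCOVA are about level (1.18 against 1.20). Nothing in the plan says which case applies.

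**A reader might also infer that the main result is at risk.** It is not. The primary ANCOVA does not use the rule, and the adjusted models are labelled secondary/exploratory. Applied mechanically, the imbalance test did not inflate false positives in simulation (3.0% to 4.8% against a nominal 5%).

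**The 0.45 SD example is not specific to the rule.** The baseline-only ANCOVA would not correct that imbalance either. The example shows only that the test is a poor safeguard.

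**Conclusion.** The point holds, for secondary/exploratory models only. A test of baseline imbalance is an uninformative way to choose covariates in a randomised trial. Here it is joined to an undefined second condition, so the adjusted model cannot be fixed in advance.

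The firm comparison is with pre-specified prognostic adjustment, which was the most precise option in every scenario that contained a prognostic covariate. Its size is an SD of about 1.23 to 1.26 against 1.06 to 1.16 mg/L, assuming 20 per arm, 15 independent candidates and one prognostic with partial r 0.3 to 0.5. No claim is made either way against the baseline-only ANCOVA.

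The same sentence also admits time-updated variables. Adjusting for changes after randomisation raises a different question, not covered here.

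**What to change.** For baseline variables, delete the criterion of a significant between-arm difference in Protocol 9.1 and the SAP. Before the arm code is released, name a small fixed set for the secondary model:

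- the baseline level of the outcome biomarker, stated as always kept (the protocol lists biomarker levels only among possible covariates, and the SAP list omits them);
- the two stratification factors, sex and regular sleep-aid use;
- one or two factors chosen on prior prognostic grounds, such as age or baseline ISI.

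Use the same list in both documents, and state that the Protocol 9.7 comparisons will not be used to select covariates.

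The change needs no new data. It gives up the freedom to add covariates after seeing the baseline table, and uses degrees of freedom: with four covariates beyond baseline, residual df fall from 37 to 33. If none of the four were prognostic, the closed form gives 1.183 × √(37/32) = 1.27 mg/L against 1.20. Together they need to explain about 1 − 32/36 = 11% of the residual variance to break even, and somewhat less because the stratification factors are near balance. The set should therefore stay short and be chosen for prognosis.

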To minimize treatment barriers, attrition, and subject burden, SHUTi sessions will be delivered remotely at a location selected by the participant where s/he can access a computer with internet, such as the participant's

home, the participant's work, a family member's/friend's home, or a public library. We will loan study tablet computers with data plans to patients without reliable internet access to maximize intervention update and decrease attrition. [name] laboratory and the Infectious Diseases Research Clinic at Eskenazi Health Hospital will serve as backup locations for SHUTi session delivery if a participant prefers in-person delivery.

We will deliver SHUTi with support, as it increases the efficacy of internet interventions (104-106). Specifically, the Intervention RA, a clinical psychology PhD mentee of [name], will track each participant's progress through the SHUTi dashboard and will check-in with each participant every two weeks to address any questions or issues.

We will also tell patients that, if they choose to complete SHUTi session where others are present, these other people (e.g., family member or friend) may realize that they are completing a treatment for insomnia. It will be up to each patient to decide if the available remote locations provide sufficient privacy. Up to 6 sessions will be completed by the participant between the Entry Visit and the Week 12 Study Visit at rate of a session every 1-2 weeks. No physiologic or biologic assessments will be performed during these sessions. The participants need not be fasting for these sessions.

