## 9.10 Analysis Datasets

Intent-to-treat set will include patients as randomized regardless their adherence status and data completeness.

Per-protocol set will include patients with 24-week hsCRP measurements and who completed at least 4 out of 6 SHUTi sessions.

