## 9.12 Subgroup Analysis

Our analyses will be repeated comparing the Active Control group with the SHUTi intervention group who complete  $\geq 4$  of the 6 planned treatment sessions (the SHUTi4-6 subgroup).

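### The engagement contrast selects only the SHUTi arm on sessions completed, so it cannot establish an engagement effect; the per-protocol set in 9.10 needs reconciling with it

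*Protocol*

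**What the plan says.** The primary analysis is an intention-to-treat ANCOVA of Week 24 biomarker level on arm and baseline level (protocol 9.1; SAP, Statistical Analyses). The passages at issue are secondary.

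- **Protocol 9.1** sets SHUTi participants with at least four of six sessions "vs. the active control group to determine if greater SHUTi engagement leads to greater differences in the endpoints of interest". It then adds: "All of these models will be repeated for comparing 12-week changes in the endpoints".
- **Protocol 9.12** lists the same contrast as a subgroup analysis: "Our analyses will be repeated comparing the Active Control group with the SHUTi intervention group who complete" four or more of the planned sessions.
- **SAP, Statistical Analyses** keeps the same purpose, "to determine if greater SHUTi engagement leads to greater differences in the endpoints of interest", but neither defines the subgroup nor gives a per-protocol set.
- **Protocol 9.10** defines the set: "Per-protocol set will include patients with 24-week hsCRP measurements and who completed at least 4 out of 6 SHUTi sessions".

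The subgroup name also varies. Sections 2.3.3 and 9.12 use SHUTi 4-6; 9.1 and the SAP use ISI 4-6, although ISI is the insomnia score.

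**The concern.** How many sessions a participant completes is decided after randomisation, and those who complete four or more may differ in health, motivation, stability or other care. The Active Control arm receives static education and four-weekly calls (5.2), and no comparable engagement rule is applied to it. The contrast therefore sets engagers against a mixture of people who would and would not have engaged. A difference can arise with no effect of SHUTi, and a real effect can be inflated or masked. No section offers a method for the selection, such as a complier estimator, weighting, or a dose model within SHUTi.

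The stake is what gets carried forward. Section 9.5 says the trial exists to supply effect sizes for a definitive trial, and 2.3.3 already highlights larger ISI reductions in a four-person subgroup defined this way. An engager estimate reported under the present wording could be taken as evidence of dose response.

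Section 9.10 adds a practical problem. The analysis-set definition is where a programmer looks first, and as written it does not describe the comparison in 9.1 and 9.12.

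**Working it through.** **1. The plan's own figure.** Section 9.5 gives hsCRP SD 4.87 mg/L, baseline to Week 24 correlation 0.64, 20 per arm, 80% power, two-sided alpha 0.05, detectable difference 3.41 mg/L.
- Residual SD after baseline adjustment: 4.87 × √(1 − 0.64²) = 3.74.
- Standard error, 20 vs 20: 3.74 × √(2/20) = 1.18.
- Detectable difference from the noncentral t distribution (37 df): 3.40, against 3.41 stated.

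The figure reproduces as an ANCOVA on all 20 vs 20, so 3.74 is the right residual SD here.

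**2. Inputs for the engagement contrast.**
- Completers: "We will enroll 50 participants with the expectation that 40 (20 in each arm) will complete the 24 week study" (9.5).
- Share engaging, p: the only basis in the documents is the small pilot in 2.3.3, where four people reached at least four sessions. That is 4 of 6 SHUTi completers (67%) or 4 of 10 randomised (40%). I use 50%, 67% and 80% of completers. The 50% figure matches 40% of 25 randomised (10 people) if all of them are among the 20 completers.
- rho, the correlation of engagement with better (lower) baseline-adjusted hsCRP: not in the documents, so assumed over a range.

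**3. Bias with no true effect.** If the share p of the SHUTi arm with the highest underlying engagement is kept, its mean engagement is φ(z)/p standard units, where z is the normal quantile for p. So bias = −rho × 3.74 × φ(z)/p. The values of φ(z)/p are 0.798, 0.545 and 0.350 at 50%, 67% and 80%.

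| rho | 50% | 67% | 80% |
|---|---|---|---|
| 0.3 | -0.90 | -0.61 | -0.39 |
| 0.2 | -0.60 | -0.41 | -0.26 |
| 0.1 | -0.30 | -0.20 | -0.13 |
| 0 | 0 | 0 | 0 |

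Units are mg/L. At rho −0.3 the signs reverse (simulated +0.89, +0.62, +0.40). If only 40% of completers engaged, bias at rho 0.3 would be −1.08.

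**4. Size against noise.** SE = 3.74 × √(1/(20p) + 1/20) = 1.45, 1.32, 1.26. At rho 0.3 the bias is therefore 0.62, 0.46 and 0.31 of a standard error. In 20,000 simulated null trials per setting (dropout not modelled), type I error was 8.9%, 6.8% and 6.1% at rho 0.3; 6.6%, 5.8% and 5.4% at 0.2; and 5.7%, 5.2% and 5.0% at 0.1. A separate simulation that kept exactly 13 of 20 gave 7.6% at rho 0.3.

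**5. The 9.10 set, read literally.** It joins two conditions: a Week 24 hsCRP value and at least four SHUTi sessions. Controls do no SHUTi sessions, so none qualifies, yet 9.1 and 9.12 both name the Active Control group as comparator.

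**6. The Week 24 condition at Week 12.** With 25 randomised and 20 completing per arm, five per arm lack Week 24 data. If all ten attended Week 12 and engagement among dropouts matched that among completers, the contrast would lose 5 + 5p people: 7.5, 8.3 or 9. The true number could be as low as zero, because Week 12 attendance is not given.

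**The case against.** The strongest reply is one of proportion. The contrast is secondary, the trial is described as exploratory and not sized for superiority testing, and the dispute turns largely on one verb. At rho 0.1 to 0.2 the error rate is only 5.0% to 6.6%, and the direction of any bias is unknown. All of that stands. It limits the weight of the point but does not make the stated inference valid.

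Four stronger readings are tempting, and the documents do not support them.

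- *That the per-protocol comparison has no control arm.* Sections 9.1 and 9.12 plainly intend controls; 9.10 simply omits the rule for them.
- *That the set fits only Week 24 hsCRP.* Section 6.2.6.6 shows that IL-6, sCD14, sCD163 and the monocyte fractions come from the same tubes as hsCRP, so the other Week 24 blood markers are largely unaffected. The mismatch is mainly at Week 12, and only if the 9.10 set is used there; neither 9.1 nor 9.12 says that it is.
- *That the adjusted models in 9.1 either cure the problem or can be shown to fail by a given amount.* Those models take "other potentially confounding baseline and time-updated variables that differ significantly between groups". The plan does not spell out whether that screen is rerun between engagers and controls, and the documents give no basis for computing how much bias it would remove. What can be said is that no such model covers unmeasured differences. Changes in ISI, which it may include, are post-randomisation and are a proposed mediator in 9.4.
- *That the trial's main result is compromised.* The primary analysis keeps everyone as randomised.

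**Conclusion.** The point holds as a correction of wording and definition. The contrast in 9.1, 9.12 and the SAP is not randomised and cannot support the conclusion that 9.1 and the SAP attach to it. Section 9.10 contradicts the comparison it is meant to serve and, if used at Week 12, would exclude people with usable data because of a later visit.

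The likely distortion is modest: about 0.4 to 0.9 mg/L at rho 0.3, about 0.1 to 0.3 at rho 0.1, none at zero, and of opposite sign if engagers have the worse prognosis. These figures assume 20 completers per arm, no true effect, normal residuals with SD 3.74, and 50% to 80% engaging. Rho is an assumption throughout, and the pilot share is too small a sample to be more than a guide to the range. The certain part, selection in one arm only, does not depend on any of these numbers.

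**What to change.** 1. In 9.10, redefine the per-protocol set as SHUTi participants with at least four of six sessions plus Active Controls, each with data for the endpoint and visit being analysed. Use one defined subgroup name in 9.1, 9.12 and the SAP.
2. In 9.1, 9.12 and the SAP, label the contrast descriptive and non-randomised. Delete from 9.1 and the SAP the statement that it determines an engagement effect.
3. Optional: report a complier-average estimate, with randomised arm as instrument for completing at least four sessions, as supportive only. State that it assumes no effect of SHUTi assignment below four sessions. That is doubtful, because the research assistant "will check-in with each participant every two weeks to address any questions or issues" in the SHUTi arm whatever the session count. State also that it is less precise than intention-to-treat and does not show a dose effect. Its standard error is roughly 1.18/p, or 2.4, 1.8 and 1.5 mg/L at 50%, 67% and 80% engaging; simulation at rho 0.3 gave 2.66, 1.87 and 1.55, against about 1.2 for intention-to-treat.

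Items 1 and 2 cost a few sentences and no new data. Item 3 needs a little programming and can be left out.
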